6.9.2. Laboratory Data

Clinical laboratory values will be expressed in SI units. Missing laboratory data will not be imputed.

Summary data for each laboratory parameter will be presented for each continuous clinical laboratory parameter (including hematology, serum chemistry, liver function tests and coagulation studies). Descriptive statistics will be presented for the actual values, change from baseline, and percent change from baseline by visit.

Shift tables will be employed to summarize the baseline category versus the “worst” post-baseline category for selected parameters.

A listing for all patients with abnormal liver function tests, defined as an ALT $>3 \times \text{ULN}$, AST $>3 \times \text{ULN}$, or total bilirubin $>2 \times \text{ULN}$ at any time point, will also be provided.

A table will be produced to summarize the number and percentage of patients in each of the below categories at any post-baseline time point.

- ALT >1 & ≤ 3 , >3 & ≤ 5 , >5 & ≤ 10 , >10 & ≤ 20 , $>20 \times \text{ULN}$;
- AST >1 & ≤ 3 , >3 & ≤ 5 , >5 & ≤ 10 , >10 & ≤ 20 , $>20 \times \text{ULN}$;
- ALT or AST >1 & ≤ 3 , >3 & ≤ 5 , >5 & ≤ 10 , >10 & ≤ 20 , $>20 \times \text{ULN}$;

- ALP > 1.5×ULN;
- Total Bilirubin >1.5 & ≤2, >2 & ≤3, >3 & ≤5 and >5×ULN;
- Total Bilirubin > 2×ULN concurrent with ALT or AST > 3×ULN.

In separate figures, the peak total bilirubin (at any time post-baseline) will be plotted against the peak AST, the peak ALT, and the peak AST or ALT levels at any time post-baseline.

For hematology and serum chemistry, summary tables of potentially clinically significant abnormalities will be provided. The results may also be graded according to the National Cancer Institute CTCAE Version 5.0 or above. A shift summary of baseline to maximum post-baseline CTCAE grade may be presented, as appropriate.

The estimated glomerular filtration rate (eGFR, mL/min/1.73 m²) will be categorized as below: ≥ 90; 60-89; 45-59; 30-44; 15-29 and < 15. A shift summary of baseline to worst post-baseline eGFR category will be presented.

All laboratory data, including pregnancy and follicle stimulating hormone (FSH) test results, will be provided in data listings. Out-of-range laboratory results will be identified in the listings.

6.9.3. Vital Signs and Physical Examination

For vital signs, descriptive statistics by visit and treatment arm will be provided for each variable. Vital sign measurements will be presented for each patient in a data listing, with abnormal vital signs flagged.

For the physical examination, clinically significant findings prior to first dose of study drug will be recorded and summarized under Medical History, unless there is an SAE in which case the event will be recorded and summarized under Adverse Events. Physical examination findings that are new or worsened after first dose of study drug will be recorded and summarized under Adverse Events.

6.9.4. Electrocardiogram

Electrocardiogram (ECG) findings will include rhythm, ventricular rate, RR interval, PR interval, QRS duration, QT interval, and corrected QT (QTc) interval. QTc interval will be calculated using Fridericia's correction formula.

$$\text{Fridericia's cube-root corrected QT: QTcF (ms)} = \text{QT (ms)} \times \sqrt[3]{\frac{\text{HR (bpm)}}{60}}.$$

RR, PR, QRS, QT, and QTcF intervals and their change from pre-dose baseline will be summarized for each treatment arm by scheduled visit. The number and percentage of patients with abnormal results (clinically significant abnormal or not clinically significant abnormal) will also be summarized by treatment arm and scheduled visit.

Patients will be categorized into ≤ 450, > 450 - 480, > 480 - 500, or > 500 ms per their maximum post-baseline absolute QTcF interval and ≤ 30, > 30 - 60, or > 60 ms per their maximum change from baseline QTcF interval. The number and percentage of subjects in each category will be summarized for each treatment arm.

All ECG data for each patient will be provided in a data listing.

6.9.5. Prior and Concomitant Medications

Prior and concomitant medications will be coded using the WHO Drug Dictionary (March 2020 or later). Prior medications include medications taken ≥ 1 time before the first dose of study drug, regardless of medication end date. Concomitant medications include medications taken ≥ 1 time on or after the first dose of study drug, regardless of medication start date. Results will be tabulated by ATC and preferred term.

When there are partial or missing dates, imputed dates will be used to determine 1) if a medication is prior or concomitant, and 2) duration of exposure to select medications, as needed. Imputed dates will not be presented in the listings.

For medications with partial start or stop dates: the first day/month will be imputed for start date, and the last day/month will be imputed for stop date. For medications with a completely missing start date, the medications will be considered as started prior to the first dose of study drug; medications will be classified as prior, concomitant or both depending on the medication stop dates. For medications with a completely missing stop date, the end of study date will be imputed.

Prior and concomitant medications will be presented in data listings. Previous tetramer stabilizer use will be listed separately.

6.10. Anti-Drug Antibody

The number and percentage of patients with confirmed positive ADA assay results at any time during study as well as at each scheduled visit will be summarized. The titer results for patients with confirmed positive ADA results will also be summarized using descriptive statistics.

ADA data and patients with confirmed positive ADA results will be presented in data listings.

6.11. COVID-19 Pandemic Impact Analyses

Additional data were collected to characterize the impact of the COVID-19 pandemic on general study conduct and disposition, and subsequently, additional analyses and summaries will be provided in acknowledgement of multiple regulatory guidances (FDA Guidance on Conduct of Clinical Trials of Medical Products during COVID-19 Pandemic: Guidance for Industry, Investigators, and Institutional Review Boards, US Food and Drug Administration, 2020; Guidance on the Management of Clinical Trials during the COVID-19 (Coronavirus) Pandemic, European Medicines Agency, 2020; Points to consider on implications of Coronavirus disease (COVID-19) on methodological aspects of ongoing clinical trials, European Medicines Agency, 2020; Statistical Considerations for Clinical Trials During the COVID-19 Public Health Emergency, US Food and Drug Administration, 2020).

Few patients were enrolled on APOLLO-B prior to the beginning of the COVID-19 global pandemic.

6.11.1. General Impact

Patients who discontinue treatment or stop study participation due to COVID-19 will be included in patient disposition summaries as described in Section 6.1.

Impact on study participation due to COVID-19, including visit completion, visit location changes, and study drug dosing changes, will be summarized overall on the patient level with both continuous and categorical descriptives, and overall and by visit on the event level with categorical descriptives. Patient- and event-level summaries of the impact on study participation due to COVID-19 may also be generated by site and/or region.

Impact on study participation due to COVID-19 will be presented in data listings by patient and by visit within patient.

6.11.2. Impact on Efficacy

Summaries of missing efficacy data due to the COVID-19 pandemic will be included in missing efficacy data summaries as described in Section 5.8.1. Patient data listings will flag assessments censored due to COVID-19.

The number and percentage of patients who died, were hospitalized or had an urgent HF visit due to COVID-19 will be summarized by treatment arm and overall. The total number of hospitalizations and urgent HF visits due to COVID-19 and the number of hospitalizations and urgent HF visits per patient due to COVID-19 will also be summarized using descriptive statistics by treatment arm and overall. Patient data listings will be presented for deaths, hospitalizations and urgent HF visits due to COVID-19.

Given the measures specified in the protocol designed to ensure data integrity, analyses excluding patients with COVID-19 related protocol deviations will not be prespecified, but may be considered post hoc, if warranted.

6.11.3. Impact on Adverse Events

An overall summary of AEs mapping to a COVID-19 custom query will include the number and percentage of patients, as well as events and event rates, with any AE, any AE assessed by the Investigator as related to treatment, any severe AE, any severe AE related to treatment, any SAE, any SAE related to treatment, any AE leading to treatment discontinuation, any study drug related AE leading to treatment discontinuation, and any deaths. AEs mapping to the COVID-19 custom query will be summarized by HLT and PT. Due to the evolving nature of COVID-19-related MedDRA terminology, the COVID-19 custom query will be based on the latest information available at the specified analysis timepoint.

AEs mapping to the COVID-19 custom query will also be presented in a data listing.

7. CHANGES TO PLANNED ANALYSES

7.1. Changes from Protocol in Original SAP

Change from Protocol	Detailed Description/Rationale
In the PK and PD Analysis Set definitions, "any amount of study drug" (as specified in the protocol) was updated to "at least one complete dose of study drug".	PK and PD data from patients who have not received at least one complete dose of study drug would not be representative of the planned dose level.

Change from Protocol	Detailed Description/Rationale
The model specified to analyze the composite endpoint of all-cause mortality and frequency of all-cause hospitalizations was updated from an Andersen-Gill model stratified by baseline tafamidis (as specified in the protocol) to an Andersen-Gill model including baseline tafamidis in the list of covariates.	Given the cap on baseline tafamidis for the study, a stratified Andersen-Gill model including several covariates may encounter convergence issues. Therefore, the model now includes baseline tafamidis use in the list of covariates.

7.2. Changes in SAP Amendment 1

The SAP Amendment 1 includes more details previously not discussed in the original SAP. Some changes to analysis methods were made following regulatory feedback. The details of the changes and rationales are listed in the table below.

Summary of Changes	Detailed Description/Rationale
Updated Figure 1	To align with protocol Amendment 3
In the protocol and original SAP, an interim assessment of the tafamidis drop-in rate was planned to assess the impact of the drop-in rate on the power of the study and the potential need to increase the sample size. This interim assessment was not conducted during the study.	Due to the low rate of tafamidis drop-in on APOLLO-B, the interim sample size reassessment was determined to be unnecessary.
Added details on estimand and handling of intercurrent events for primary and secondary endpoints. The primary analyses for efficacy endpoints were also updated to not censor observations after tafamidis drop-in or after missing doses due to COVID-19.	Updates made following regulatory feedback
Updated primary MMRM model specification	To align with protocol Amendment 3
Changed imputation approach in PMM model for patients who die (not due to COVID-19) or who become unable to walk due to progression of ATTR amyloidosis by Month 12	Update was made since such patients are not expected to behave in the same way as those who remain in the study on treatment and therefore require a different imputation approach.
Updated PMM appendix	To clarify the imputation procedure for the missing data patterns, including imputation for death/inability to walk as noted above
Updated data handling approach for tafamidis drop-in and missing doses due to COVID-19 in MMRM and binary sensitivity analyses	To align with updates made to the intercurrent event handling strategies for the estimand
Updated specification for the Andersen-Gill model to be stratified by baseline tafamidis use	To align with the protocol
The Poisson model for analysis of the frequency of hospitalizations and urgent HF visits was	This update was made to allow for potentially different treatment effects between the baseline tafamidis use (yes/no) subgroups.

Summary of Changes	Detailed Description/Rationale
updated to add the treatment-by-baseline tafamidis use interaction.	
Updated the subgroup analysis MMRM model specification	This update was made to allow for potentially different treatment effects between the baseline tafamidis use (yes/no) subgroups.
Removed statement that ECG parameters will be treated as missing if QRS duration is >120 ms	To maintain consistency with analyses conducted in other studies in the patisiran clinical development program
Removed description of efficacy and safety summaries by pandemic phase	Summaries by pandemic phase will not be performed since limited data are available prior to the start of the pandemic and limited post-pandemic data are anticipated at the time of the primary analysis.

7.3. Changes in SAP Amendment 2

The SAP Amendment 2 includes changes to the primary and sensitivity analyses of 6-MWT as well as additional updates. The details of the changes and rationales are listed in the table below.

Summary of Changes	Detailed Description/Rationale
Added composite endpoint for all-cause mortality and frequency of all-cause hospitalizations and urgent HF visits in patients not on tafamidis at baseline as a secondary endpoint	The APOLLO-B study enrolls patients who are tafamidis-naïve as well as patients who are on tafamidis and have demonstrated disease progression in the opinion of the Investigator. The subgroup of tafamidis-naïve patients is a more homogeneous subpopulation while patients on baseline tafamidis are expected to be more heterogeneous (eg, in terms of duration of prior tafamidis treatment). It's anticipated that a larger treatment effect could be observed in tafamidis-naïve patients compared to patients on baseline tafamidis. The composite outcome endpoint defined in all patients in the Full Analysis Set is the only secondary endpoint that is not sufficiently powered to detect a treatment difference. Since the majority of patients (75%) are tafamidis-naïve, defining the composite outcome endpoint in this more homogeneous, enriched subgroup could improve the power and precision of the estimated treatment effect.
Changed primary analysis of 6-MWT from MMRM to the stratified Wilcoxon Rank Sum test with HL estimate of the median treatment difference. The MMRM model for 6-MWT was moved to be a sensitivity analysis.	Parametric methods, such as MMRM or ANCOVA, may be sensitive to violations of the normality assumption (eg, skew, outliers) whereas nonparametric methods, such as Wilcoxon Rank Sum test or rank ANCOVA, are more robust to such violations. Based on review of blinded 6-MWT data in APOLLO-B, the normality assumption does not appear to hold. In addition, BridgeBio recently reported 6-MWT data in ATTR cardiomyopathy which showed an apparent deviation from normality with the median differing from the mean for the change from baseline in 6-MWT at Month 12. A literature search of past Phase 3 studies with 6-MWT endpoint also showed that normal assumptions often did not hold for this endpoint, and a non-parametric method was commonly used as the primary analysis. Given these considerations, the primary analysis method was therefore updated to the stratified Wilcoxon Rank Sum test.
Intercurrent event handling strategy updated for 6-MWT	For the primary analysis of 6-MWT, patients who die or who lose the ability to walk due to progression of ATTR amyloidosis will now be imputed as the worst possible change for the patient (ie, 0 – baseline 6-MWT).
Updated Section 6.6.2.1	Updated the text in the KCCQ-OS section since the prior version referenced the planned 6-MWT analyses, which have since been changed. The planned KCCQ-OS analyses in these sections are unchanged from the SAP Amendment 1.
Added binary analysis for KCCQ-OS	To quantify and compare the proportion of patients in each treatment group who maintain or improve in their KCCQ-OS score in the 12m-DB period.

Summary of Changes	Detailed Description/Rationale
Updated planned subgroup analyses	
The HL estimate of the median difference between patisiran and placebo will be used for subgroup analyses of 6-MWT to align with the primary analysis.
 
Clarified that the MMRM model used for the baseline tafamidis use subgroup analysis for KCCQ-OS is the same as the primary MMRM model for KCCQ-OS since these subgroup estimates can be obtained directly from the primary model.

Removed summaries for SAEs by maximum severity and by maximum relationship	Table summaries determined to be unnecessary as this can be assessed by reviewing the SAE listing.
Removed summaries for AEs/SAEs leading to study discontinuation	Patients who discontinue the study due to a TEAE are accounted for in the disposition summary. Given the overlap between TEAEs that led to treatment discontinuation and those that led to study withdrawal, it is not considered necessary to list/tabulate the AEs that led to study withdrawal.
Removed NYHA from list of covariates for ANCOVA models of echo parameters and Norfolk QoL-DN Total Score	To create a more parsimonious model
Added LV relative wall thickness, LV end-diastolic volume, and cardiac output to list of selected echo parameters to be analyzed by ANCOVA	To conduct a more comprehensive echocardiographic evaluation of differences between treatment groups in cardiac structure and function
Removed summary of PK exposure by mortality status.	Sparse PK samples are collected in APOLLO-B and relating these exposures to mortality may not provide meaningful interpretation of results. A separate safety exposure analysis using population PK-PD modeling may be conducted, if deemed necessary.

7.4. Changes in SAP Amendment 2.1

SAP Amendment 2.1 addresses regulatory feedback received from the FDA on SAP Amendment 2. The main changes in SAP Amendment 2.1 include an update to the population-level summary estimate for 6-MWT and a change to the imputed 6-MWT distance for patients who die or who lose the ability to walk due to progression of ATTR amyloidosis. The details of the main changes, including other additional updates, and rationales for the changes are listed in the table below.

Summary of Changes	Detailed Description/Rationale
Updated population-level summary estimate from unstratified Hodges-Lehmann estimate to stratified Hodges-Lehmann estimate	Update made following regulatory feedback to use HL estimate stratified by baseline tafamidis use, which is consistent with the planned stratified Wilcoxon rank sum test.
Updated imputed values for patients who die or who lose the ability to walk due to progression of ATTR amyloidosis	Update made following regulatory feedback. For the primary analysis of 6-MWT, patients who die or who lose the ability to walk due to progression of ATTR amyloidosis will now be imputed as the worst 10 th percentile change observed across all patients in the 12m-DB period, capped by the worst possible change for the patient (ie, 0 – baseline 6-MWT). This is expected to be less influential on the estimated treatment effect than simply imputing the worst possible change for these patients.
Added condition that 6-MWT assessments where the timer was stopped after ≤ 4 minutes will be excluded from analyses	Exclude assessments that were improperly conducted
Updated windowing rule for longitudinal efficacy assessments for patients randomized to patisiran	To allow assessments collected shortly after first OLE dose to be summarized with Month 12 assessments in order to reduce the amount of missing data. Efficacy endpoints are not expected to be meaningfully impacted within a short time after the first dose in the OLE period.
Added treatment-by-baseline tafamidis use interaction term to echo and Norfolk ANCOVA models	To allow for potentially different treatment effects between the baseline tafamidis use (yes/no) subgroups.
Added Section 5.9	To clarify that the primary analysis for endpoints related to hospitalizations and urgent HF visits will be based on CEC adjudication results

9. APPENDICES

9.1. Detailed Statistical Methodology for the Control-based Imputation for Missing Data

Patients are classified into five patterns for missing data at Month 12:

1. Patients who have missing data due to COVID-19: missing data will be assumed to be MAR and imputed by using MI estimated from the treatment arm and baseline tafamidis use group to which the patient was randomized. This pattern includes:
 - a. Patients who miss the Month 12 assessment due to COVID-19
 - b. Patients who have a serious COVID-19 AE or who die due to COVID-19 before Month 12
2. Placebo patients who do not have missing data due to COVID-19 and are alive through the 12m-DB period and have not become unable to walk due to progression of ATTR amyloidosis by Month 12: missing data will be assumed to be MAR and imputed by using MI estimated from placebo patients in the baseline tafamidis use group to which the patient belongs.
3. Patisiran patients who do not have missing data due to COVID-19 and are alive through the 12m-DB period, have not become unable to walk due to progression of ATTR amyloidosis by Month 12, and have missing data with the last dose of study drug received within 60 days of the scheduled time point: missing data will be assumed to be MAR and imputed by using MI estimated from on-treatment patisiran patients in the baseline tafamidis use group to which the patient belongs.
4. Patisiran patients who do not have missing data due to COVID-19 and are alive through the 12m-DB period, have not become unable to walk due to progression of ATTR amyloidosis by Month 12, and the last dose of study drug was received more than 60 days prior to the scheduled time point: missing data will be assumed to be MNAR and imputed (using data from placebo patients in the baseline tafamidis use group to which the patient belongs) using the copy reference (CR) approach.
5. Patients who die (including heart transplant and ventricular assist device placement) during the 12m-DB period (not due to COVID-19) or who have become unable to walk due to progression of ATTR amyloidosis by Month 12: missing data will be assumed to be MNAR and imputed as the worst 10th percentile change observed across all patients in the 12m-DB period, capped by the worst possible change for the patient (ie, 0 – baseline 6-MWT).

For patients who are alive through the 12m-DB period and who have not become unable to walk due to progression of ATTR amyloidosis, all missing data for the placebo arm and missing data for the patisiran arm during the on-treatment period (ie, assessments within 60 days of the last dose of study drug) will be imputed using MI under the MAR assumption. Since the pattern of missing data within patients may be non-monotone, multiple imputation will be conducted separately by treatment arm and baseline tafamidis use group using the Markov Chain Monte Carlo (MCMC) method. For each treatment arm/baseline tafamidis use group, the imputation model will include type of amyloidosis (hATTR vs. wtATTR), NYHA class (I/II vs. III), age at randomization (<75 vs. ≥75), NT-proBNP (≤3000 ng/L vs >3000 ng/L), baseline 6-MWT, and

all calculated values of change from baseline in 6-MWT at pre-specified visits. The input dataset DATAIN will exclude data from patients in pattern 5 above and exclude data from patisiran patients that were collected after treatment discontinuation (ie, more than 60 days after the last dose of study drug). Below is a sample SAS code for the multiple imputation:

```
proc mi data=DATAIN out=DATA_STEP1 seed=234 nimpute=100;
  by treatment bltaf;
  em maxiter=300 converge=1e-4 itprint outem=outem;
  var baseline_variables 6MWT_base 6MWT_chg_m6 6MWT_chg_m9 6MWT_chg_m12;
  mcmc chain=multiple initial=em;
run;
```

The MI procedure generates imputed values for all missing values. For patisiran patients, the imputed data from the on-treatment period will be kept while the imputed data after treatment discontinuation will be discarded and replaced by either the observed non-missing values (if available) or the imputed values using the CR approach described below. The imputation model will include type of amyloidosis (hATTR vs. wtATTR), NYHA class (I/II vs. III), age at randomization (<75 vs. ≥75), NT-proBNP (≤3000 ng/L vs >3000 ng/L), baseline 6-MWT, and all calculated values of change from baseline in 6-MWT at pre-specified visits.

```
proc mi data=DATA_STEP1_2 out=DATA_STEP2 nimpute=1 seed=xxx;
  by _imputation_ bltaf;
  class treatment;
  fcs nbiter=30 reg (6MWT_chg_m12 = baseline_variables 6MWT_base
    6MWT_chg_m6 6MWT_chg_m9);
  mnar model (6MWT_chg_m12 / modelobs=(treatment='placebo'));
  var baseline_variables 6MWT_base 6MWT_chg_m6 6MWT_chg_m9 6MWT_chg_m12;
run;
```

Finally, for patients in pattern 5, missing Month 12 6-MWT change from baseline values will be imputed as the worst 10th percentile change observed across all patients in the 12m-DB period, capped by the worst possible change for the patient (ie, 0 – baseline 6-MWT).

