6.6.1.3. Sensitivity Analyses

Sensitivity analyses will be conducted using the following methods to assess the impact of missing data and the robustness of the primary analysis.

Sensitivity Analysis 1: Stratified Wilcoxon Rank Sum Test Including All Censored Data

A sensitivity analysis including all 6-MWT assessments (ie, not treating assessments that occur on or after the onset of a serious COVID-19 AE as missing) will be conducted using the same analyses as specified in Section 6.6.1.2.

Sensitivity Analysis 2: Stratified Wilcoxon Rank Sum Test with Control-based Imputation for Missing Data in Off-treatment Patisiran Patients

A sensitivity analysis will be performed using the stratified Wilcoxon Rank Sum test where missing data from off-treatment patisiran patients are imputed based on data from the placebo group. This accommodates situations where the missingness mechanism may be missing not at random (MNAR). The model will be based on the following assumptions for missing data at Month 12:

1. Patients who have missing data due to COVID-19, including patients who have missing assessments due to COVID-19, or who have a serious COVID-19 AE or who die due to COVID-19 prior to the Month 12 assessment will be imputed assuming data are MAR.

Under the hypothetical estimand of interest where the COVID-19 pandemic did not occur, these assessments should have been obtained with no COVID-19 impact. Missing data meeting these criteria will be imputed separately for each treatment arm and baseline tafamidis use group using multiple imputation (MI) estimated from all non-missing data collected within each group.

2. For patients who have missing data unrelated to COVID-19, who are alive through the 12m-DB period and who have not become unable to walk due to progression of ATTR amyloidosis by Month 12, the imputation will be performed by baseline tafamidis use (yes/no) separately based on different patterns described as below:
 - a. Placebo patients who have missing data: The missing data are considered MAR and will be imputed using multiple imputation (MI) estimated from placebo patients. The imputation is done regardless of whether a patient was on-treatment or discontinued treatment before the scheduled efficacy assessment.

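### Appendix 9.1 defines COVID-19 missingness as MAR within the patient's own arm, but its imputation step, read literally, sends some of those patisiran patients to placebo-based copy reference

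*SAP*

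**What the plan says.** All references are to SAP Amendment 2.1.

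**The definitions.** Section 6.6.1.3, Sensitivity Analysis 2, item 1 covers assessments missed because of COVID-19, serious COVID-19 AEs and COVID-19 deaths. It ends: "who die due to COVID-19 prior to the Month 12 assessment will be imputed assuming data are MAR". It continues: "Missing data meeting these criteria will be imputed separately for each treatment arm and baseline tafamidis use group using multiple imputation (MI) estimated from all" the non-missing data in that group. Appendix 9.1 repeats this as pattern 1, whose members include "Patients who have a serious COVID-19 AE or who die due to COVID-19 before Month 12". The pattern 1 rule is "missing data will be assumed to be MAR and imputed by using MI estimated from the treatment arm and baseline tafamidis use group to which" each patient belongs by randomization. Neither place sets a condition on time since the last dose.

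Pattern 4 is the only copy-reference pattern. It opens "Patisiran patients who do not have missing data due to COVID-19 and are alive through the 12m-DB period, have not become unable to walk due" (the cause named there is disease progression), and it requires a last dose more than 60 days before the scheduled time point. Item 2 of Section 6.6.1.3, which contains the copy-reference rule, is likewise confined to missingness unrelated to COVID-19.

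**The implementation.** Later in Appendix 9.1, the input dataset for the first imputation leaves out pattern 5 patients and patisiran data "collected after treatment discontinuation (ie, more than 60 days after the last dose of study drug"). After that imputation, for patisiran patients generally, on-treatment imputed values stay, but the text says of the later ones: "the imputed data after treatment discontinuation will be discarded and replaced by either the observed non-missing values". The discarded values give way to observed values where there are any, and otherwise to copy reference, with Month 12 modelled from placebo observations.

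**The concern.** The definitions sort patients by the reason for missingness. The implementation step sorts patisiran values by time since the last dose. The two disagree for a patisiran patient whose data are missing because of COVID-19 and who is more than 60 days past the last dose.

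The stated aim of item 1 is the hypothetical in which the pandemic did not occur. Under the literal step, some COVID-19 missingness in the patisiran arm is handled as treatment dropout, and none in the placebo arm is. Two programmers could follow the same appendix and produce different Sensitivity Analysis 2 results. The KCCQ-OS pattern mixture model (Section 6.6.2.1.3) takes over the same missing-data assumptions, so it is exposed too if it is programmed with the same steps.

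**Working it through.** **1. Cases traced under both texts (Month 12 value).**

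- *Patisiran, dosing continues, Month 12 visit missed because of COVID-19.* Definition: own-arm MAR. Step: within 60 days of the last dose, so the value is kept. They agree.
- *Patisiran, COVID-19 death at about Month 6.* Definition: pattern 1, own-arm MAR. Step: roughly half a year past the last dose, so the value is discarded; nothing was observed, so copy reference from placebo applies. **They conflict.**
- *Placebo, COVID-19 death at about Month 6.* Definition: own-arm MAR. Step: such deaths are not in pattern 5, so the patient enters the first imputation, and no placebo value is discarded. They agree.
- *Patisiran, dropout unrelated to COVID-19, more than 60 days past the last dose, alive, able to walk, no Month 12 walk.* Definition: pattern 4, copy reference. Step: copy reference. They agree.
- *Patisiran, more than 60 days past the last dose, serious COVID-19 AE, Month 12 walk recorded afterwards.* Definition: pattern 1, own-arm MAR. Step: the recorded walk could be restored as an observed value. **Unclear.**

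The sample code does not settle this. The second call has no pattern variable. It applies the placebo model to whatever Month 12 values are still missing, so the discard sentence alone decides who receives copy reference.

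**2. Who can be reached.** Assumptions: doses every 3 weeks from Day 1, Month 12 at Day 365, no dosing after the COVID-19 event.

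- Last dose at Week 45 (Day 316): 365 − 316 = 49 days, within the limit.
- Last dose at Week 42 (Day 295): 365 − 295 = 70 days, beyond it.
- An event on any of Days 1 to 315 therefore leaves the patient beyond 60 days. If event timing is uniform, that is 315/365 = 86% of such events.
- If the last scheduled dose is at Week 51, a patient who is only missing infusions needs three in a row missed (Weeks 45, 48 and 51), plus a missing Month 12 walk.

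**3. Design figure (Section 5.1).** Inputs: 300 patients randomized 1:1, SD 75 m, two-sided alpha 0.05.

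- Weighted effect: 0.7 × 33 + 0.3 × 20 = 29.1 m, stated as about 29 m.
- Standard error: 75 × √(2/150) = 8.66 m.
- Power: Φ(29/8.66 − 1.96) = Φ(1.389) = 91.8%, which agrees with the stated figure of more than 90%.

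**4. Size.** If *k* of 150 patisiran patients move from own-arm imputation to placebo and each loses the full 29 m, the mean difference falls by 29 × *k*/150. The SAP gives no *k*, so a range is shown:

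- *k* = 1: 0.19 m
- *k* = 3: 0.58 m
- *k* = 5: 0.97 m
- *k* = 10: 1.93 m

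The copy-reference model conditions on baseline and on the Month 6 and Month 9 changes, so part of the effect can carry through. If half is retained, the losses are 0.10, 0.29, 0.48 and 0.97 m. Against a standard error of 8.66 m, even the full 1.93 m is about 0.22 standard errors.

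**The case against.** The best defence is that the pattern list governs. Section 6.6.1.3 items 1 and 2 and Appendix 9.1 patterns 1 and 4 all keep COVID-19 missingness out of copy reference. The later paragraph implements those patterns, its code is labelled as a sample, and one sentence merely fails to repeat an exclusion. This shows what was intended. It does not remove the conflict: Section 6.6.1.3 sends the reader to the appendix for implementation, the sentence is phrased for patisiran patients generally, and the same appendix handles pattern 5 by number, so keying a step to a pattern was available.

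Several stronger readings are tempting, and the documents do not support them:

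- *Every off-treatment patisiran value becomes placebo-based.* No. Observed values are restored, and COVID-19 patients within 60 days of the last dose keep their own-arm value.
- *The SAP prescribes placebo imputation for COVID-19 missingness.* No. Four explicit rules say otherwise; the texts contradict each other.
- *COVID-19 deaths drop out of the imputation in both arms.* The MAR sentence in the appendix does name only patients alive through the double-blind period. But the first imputation excludes only pattern 5 patients and off-treatment patisiran data, so COVID-19 deaths enter it, and placebo deaths keep the result.
- *Sensitivity Analysis 2 is the only departure from MAR for dropout.* The binary analysis in Section 6.6.1.4 keeps patients with non-COVID-19 missing data in the denominator and excludes those missing because of COVID-19.
- *Each affected patient costs 29 m, always against patisiran.* The 29 m is a ceiling on a mean scale, while the planned estimate is Hodges-Lehmann. The direction holds only if patisiran works.

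**Conclusion.** The point stands as an internal contradiction of low severity. Coded as written, the replacement step in Appendix 9.1 gives a result contrary to pattern 1 and to item 1 of Section 6.6.1.3, for patisiran patients only. It applies where three conditions meet: missingness due to COVID-19, more than 60 days since the last dose, and no observed Month 12 value. Restoring walks recorded after a serious COVID-19 AE is a related gap in the same sentence.

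The effect is probably small: at most about 0.19 m per affected patient on a mean scale, using the planned 29 m and 150 per arm, with the number of patients unknown. It pulls toward no difference if patisiran works. It reaches Sensitivity Analysis 2 of the 6-MWT, and the KCCQ-OS pattern mixture model if that uses the same steps. The primary analysis in Section 6.6.1.2 has no such replacement step and is not affected. A shift of this size does not by itself show that Sensitivity Analysis 2 would be uninterpretable.

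**What to change.** Reword the replacement step in Appendix 9.1 so that it follows the patterns:

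- Copy-reference values replace first-step imputed values only for patients in pattern 4.
- Patients in pattern 1, including COVID-19 deaths, keep their own-arm MAR imputation whatever the time since the last dose. The opening of the MAR paragraph should name them.
- Observed off-treatment patisiran values are still restored, except assessments on or after a serious COVID-19 AE, which remain missing and are imputed under pattern 1.

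The third line is needed because patients with an observed off-treatment walk have nothing missing and so are not in pattern 4. Adding the words for pattern 4 alone would leave their observed values without a rule. Section 6.6.2.1.3 should say whether the KCCQ-OS model uses the same steps.

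The cost is a few sentences and a small change to the imputation program. No new data are needed, and the sample size and primary analysis do not change.
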